11.2.1 Assessment

The investigator is responsible for the detection and documentation of events meeting the criteria and definition of an AE or SAE described previously. At each visit, the subject will be allowed time to spontaneously report any issues since the last visit or evaluation. The investigator will then monitor and/or ask about or evaluate AEs using nonleading questions, such as

- “How are you feeling?”
- “Have you experienced any issues since your last visit?”
- “Have you taken any new medications since your last visit?”

Any clinically relevant observations made during the visit will also be considered AEs. In addition, although local tolerability will be assessed on a 0-3 scale, all application site reactions should be recorded as AEs.

The Tolerability Assessments Form at each visit collects a numeric severity score by body area for erythema, stinging/burning, and pruritus.

In addition, if skin irritation is more than the expected erythema, stinging/burning, and pruritus with the application of this topical retinoid (i.e., clinically relevant), please enter the application site reactions in the Adverse Event description section. If a diagnosis is known, record the diagnosis. If a diagnosis is known and there are other signs/symptoms that are not generally part of the main diagnosis, record the diagnosis and each sign/symptom on a separate line. If a diagnosis is not known, record each sign/symptom on a separate line. Examples are allergic contact dermatitis, sunburn, skin erosion, and swelling.

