10.3.4.2.4 Other Safety Variables

Local tolerability will be assessed on a 0-3 scale (none, mild, moderate, severe). All application site reactions will be recorded as TEAEs in the diary. These should include the date and severity of the TEAE.

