11.1.5 Significant Adverse Events

Other significant AEs are defined as marked hematological and other laboratory abnormalities (other than those meeting the definition of serious) and any events that led to an intervention, including withdrawal of test drug, dose reduction, or significant additional concomitant therapy.

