11.3. Special Considerations

11.3.1 Adverse Events of Special Interest

Since topical retinoids are associated with local application site AEs, particularly when beginning treatment, these events will be followed closely during the study and considered AEs of special interest (AESIs).

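### Section 11.2.1 gives two different rules for when an application site reaction is entered as an adverse event, so AE and AESI counts by arm can mix two definitions

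*Protocol*

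**What the plan says.** Three statements in the protocol govern when a local reaction becomes an AE.

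- Section 11.2.1, unconditional: although tolerability is scored on a 0-3 scale, "all application site reactions should be recorded as AEs".
- Section 10.3.4.2.4, also unconditional: "All application site reactions will be recorded as TEAEs in the diary".
- Section 11.2.1, two paragraphs after its first statement, conditional: "if skin irritation is more than the expected erythema, stinging/burning, and pruritus with the application of this topical retinoid (i.e., clinically relevant", and in that case "please enter the application site reactions in the Adverse Event description section". The examples that follow are allergic contact dermatitis, sunburn, skin erosion and swelling.

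Between the two statements in 11.2.1 stands the separate capture route: "The Tolerability Assessments Form at each visit collects a numeric severity score by body area for erythema, stinging/burning, and pruritus".

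Other sections depend on the answer. Section 11.1.5 counts as significant AEs "any events that led to an intervention, including withdrawal of test drug, dose reduction". Section 11.3.1 says of local application site events that "these events will be followed closely during the study and considered AEs of special interest (AESIs". Section 13.1.6.2 tabulates subjects with AEs by treatment group, with summaries by severity and relationship and a separate summary of AEs that led to discontinuation. The texts of Amendments 2 and 3 read the same on all of this.

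**The concern.** If every application site reaction is already an AE, the condition in 11.2.1 does nothing. If the condition does something, the earlier sentence and 10.3.4.2.4 are not true as written. A site coordinator faced with mild or moderate erythema after an application can defend either entering it or leaving it on the tolerability form alone.

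Safety against vehicle is part of the primary objective (Section 6.1). Local irritation is the harm on which Section 9.4 builds its application rules and which 11.3.1 singles out. The number of subjects with such an AE, its severity and the action taken would then depend partly on how each site read one page of the protocol. An analysis plan could not repair this, because it works on the entries made and cannot restore those that were not.

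**Working it through.** No figure in the protocol bears on this. It states no expected rate of application site reactions and no proportion that would count as more than expected. The check is therefore a comparison of the texts.

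**1. What each rule counts.**

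| | Unconditional (11.2.1 first statement; 10.3.4.2.4) | Conditional (11.2.1 second statement) |
|---|---|---|
| Trigger for AE entry | Any application site reaction | Irritation beyond the three expected signs |
| Grade that separates expected from more than expected | Not needed | None given |
| Subjects counted | All with any reaction | Only those above an undefined threshold |

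The second set lies inside the first. The gap is every subject whose irritation stayed within what the rater thought expected.

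**2. A reaction that changes application.** Section 9.4 reduces application to once weekly on an area scored 2 and suspends it on an area scored 3. Section 11.2.2.3 defines a reduced dose as a reduced frequency of application, so the score-2 case is a dose reduction in the protocol's own terms. Section 11.1.5 makes an event leading to dose reduction a significant AE. Under the conditional rule, a rater who regards that erythema as expected of a retinoid need not enter it. No text says that a score of 2 or 3 is by definition more than expected.

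**3. What is recorded under either rule.** Tolerability is scored at Baseline, Days 14, 30, 60 and 90 (Table 2-1) and Days 104, 120, 150 and 180 (Table 2-2). Section 13.1.6.1 summarizes it by period, treatment group and visit. Subjects note reactions in diaries (Section 7.1), and dosing changes go in the diary and the eCRF (Section 9.4).

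**4. What depends on the rule.** Start and stop dates, relationship, action taken and outcome are items of the AE record (Section 11.2.3). The tables of Section 13.1.6.2 are built from those records. The tolerability form is not scheduled at the Day 7 and Day 45 calls, nor at Day 194, while the treatment-emergent window runs to 14 days after the last application (Section 11.1.6).

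**5. Size.** Write *p* for the true proportion with a reaction in an arm and *c* for the fraction of those entered as AEs. The recorded difference from vehicle is *c*(active) × *p*(active) − *c*(vehicle) × *p*(vehicle). Under the unconditional rule, fully followed, both *c* equal 1. If sites mix rules but *c* is the same in both arms, the difference becomes *c* × [*p*(active) − *p*(vehicle)], that is, shrunk by *c*. The documents fix neither *p* nor *c*, so *c* can lie anywhere from 0 to 1 and no numerical size follows. Randomization is not blocked by center (Section 9.6), so the mix of site readings need not balance exactly across arms.

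**The case against.** The strongest reply is that the conditional text adds guidance and cancels nothing. It opens as an addition, does not use the word only, and goes on to explain how to write up diagnoses and separate signs. Its examples lie outside the three scored signs. The amendment log gives the reason as specifying how tolerability is collected. Scoring expected irritation on a dedicated form and keeping AE entry for clinically relevant excess is a coherent design. The same section also makes any clinically relevant observation an AE, and 11.1.5 points towards recording a reaction that forces a dosing change.

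Much of this stands. It makes the conflict milder, and it means that a reaction changing application may be caught by another route. It does not remove the conflict: exceeding the expected is written as the trigger for entry, while the other two statements have no trigger. If the coherent design is what was meant, those two statements have to change.

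A reader might go further and infer that the harm signal shrinks or vanishes through the recording rule. The documents do not support that. Local tolerability is a named safety endpoint (synopsis), scored and summarized by arm under either rule.

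A reader might also infer that the active arms are under-recorded preferentially, because the threshold is set by what a retinoid is expected to do. That could happen if raters guess allocation, but raters are blinded and packaging is matched (Sections 9.7 and 9.12.2). Nothing in the protocol shows differential recording.

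**Conclusion.** The contradiction is real and stands in current text. It affects AE, TEAE and AESI counts for local reactions, their severity and relationship summaries, and the action-taken data, all of which could mix two definitions across about 40 sites. It does not affect the tolerability scores at clinic visits, so the trial keeps a consistent by-arm measure of erythema, stinging/burning and pruritus.

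The size of the effect on AE counts cannot be derived from the protocol, and the direction of any bias between arms is not established. Section 13.1.6 plans no formal inference on safety variables, so no planned test turns on it. What is at stake is whether the AE tables can be interpreted and whether they agree with 11.1.5 and 11.3.1. The conclusion rests on one reading: that a stated threshold for AE entry leads at least some sites to leave out reactions below it.

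**What to change.** Reconcile Sections 10.3.4.2.4 and 11.2.1 to a single recording rule. The option that agrees best with 10.3.4.2.4, 11.1.5 and 11.3.1 is to record every application site reaction as an AE, and at minimum every reaction that leads to a change in application under 9.4. The more-than-expected judgment then becomes a separate yes/no flag on the AE page, so the distinction the added text wanted is kept and no event is dropped. If the sponsor prefers a threshold, it should be defined by grade, and the unconditional sentences in both sections should be withdrawn.

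Tell sites by memo. Before database lock, query entries already made against the diary and the tolerability form, so that all sites end on the same rule.

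The cost is a short amendment, a memo and a round of queries. The downside is more AE entries and less favourable reported AE rates.

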11.2.2 Evaluation

11.2.2.1 Severity of Adverse Events

The clinical severity of an AE will be classified as follows:

Mild	Usually transient and may require only minimal treatment or therapeutic intervention. The event does not generally interfere with usual activities of daily living.
Moderate	Usually alleviated with additional specific therapeutic intervention. The event interferes with usual activities of daily living, causing discomfort but poses no significant or permanent risk of harm to the subject.
Severe	Interrupts usual activities of daily living, or significantly affects clinical status, or may require intensive therapeutic intervention.

It is important to distinguish between severe AEs and SAEs. Severity is a classification of intensity whereas an SAE is an AE that meets serious criteria, as described in Section 11.1.4.

11.2.2.2 Seriousness

The investigator is to evaluate whether the AE meets serious criteria, as described in Section 11.1.4.

11.2.2.3 Action(s) Taken

All AEs will be treated/managed according to standard practice. The following actions may be taken with regard to the IP. Section 9.4 describes dose adjustment and stopping rules for individual subjects.

Action(s) taken may consist of the following:

Dose not changed	An indication that a medication schedule was maintained.
Dose reduced	An indication that a medication schedule was modified by reducing the frequency of application.
Drug interrupted	An indication that a medication schedule was modified by temporarily terminating a prescribed regimen of medication.
Drug withdrawn	An indication that a medication schedule was modified through termination of a prescribed regimen of medication.
Not applicable	Determination of a value is not relevant in the current context.
Unknown	Not known, not observed, not recorded, or refused.

11.2.2.4 Outcome at the Time of Last Observation

The outcome of an AE at the time of last observation will be classified as follows:

- Recovered/resolved
- Recovered/resolved with sequelae
- Recovering/resolving
- Not recovered/not resolved
- Fatal*
- Unknown

*Only select fatal as an outcome when the AE results in death. If more than one AE is judged to be possibly related to the subject's death, the outcome of death should be indicated for each such AE. Although "fatal" is usually an event outcome, events such as sudden death or unexplained death should be reported as SAEs.

11.2.2.5 Adverse Event Relationship to Investigational Product

The investigator must make an assessment of each AE's relationship to the IP. The categories for classifying the investigator's opinion of the relationship are as follows:

Not related	An AE with sufficient evidence to accept that there is no causal relationship to IP administration (e.g., no temporal relationship to drug administration, because the drug was administered after onset of event; investigation shows that the drug was not administered; another cause was proven.)
Unlikely related	An AE, including laboratory test abnormality, with a temporal relationship to IP administration that makes a causal relationship improbable, and in which other drugs, events, or underlying disease provide plausible explanations.
Possibly related	An AE with a reasonable time sequence to administration of the IP, but that could also be explained by concurrent disease or other drugs or events. Information on drug withdrawal may be lacking or unclear.
Related	An AE occurring in a causal plausible time relationship to IP administration that cannot be attributed to a concurrent disease or other drugs, chemicals, or events. The AE relationship to the IP must be assessed separately by the investigator and Mayne Pharma LLC.

11.2.3 Documentation

Any AE that occurs during the Screening Period will be captured as on the AE page of the eCRF (not medical history). All AEs that occur within the period of observation for the study must be documented in the eCRF with the following information, where appropriate. (The period of observation for the study is described in Section 11.2.)

- AE name or term
- When the AE first occurred (start date and time)
- When the AE stopped (stop date and time or an indication of “ongoing”)
- Severity of the AE
- Seriousness (hospitalization, death, etc.)
- Actions taken
- Outcome
- Investigator opinion regarding the AE relationship to the IP(s)

11.2.4 Treatment of Adverse Events

Adverse events that occur during the study will be treated, if necessary, by established standards of care. If such treatment constitutes a deviation from the protocol, the subject may be withdrawn for treatment but continue to be followed for efficacy and safety in the study. The decision about whether the subject may continue in the study will be made by the sponsor after consultation with the investigator and/or medical monitor.

If AEs occur in a subject that are not tolerable, the investigator must decide whether to stop the subject’s involvement in the study and/or treat the subject. Special procedures may be recommended for the specific IP, such as the collection of a serum sample for determining blood concentrations of IP, specific tapering procedures, or treatment regimens, as appropriate.

It is not necessary to unblind a subject’s treatment assignment in most circumstances, even if an SAE has occurred. If unblinding is necessary, see Section 9.6 for a description of the unblinding procedures.

11.2.5 Follow-up

Any AE will be followed (up to a maximum of 14 days after the last dose of IP) to a satisfactory resolution, until it becomes stable, or until it can be explained by another known cause(s) (i.e., concurrent condition or medication) and clinical judgment indicates that further evaluation is not warranted. All findings relevant to the final outcome of an AE must be reported in the subject’s medical record and recorded on the eCRF page.

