10.2.3 Follow-up Telephone Call (± 14 days after Day 90) – Only Subjects Who Do Not Continue into Open-label Extension

Clinic staff will telephone subjects who choose not to continue into the Open-label Extension within 14 days after Day 90 to assess any ongoing AEs.

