10.2.4.6 Visit 10 (Day 180 ±7 days) or Early Termination

The following procedures will be performed at this study clinic visit:

1. Perform a physical examination.
2. Record vital signs (blood pressure and pulse).
3. Record concomitant medications and concomitant therapies.
4. Record IGA.
5. Record VIIS.
6. Assess roughness.

7. Record palm/sole assessment.
8. Record palm/sole assessment of fissuring.
9. Record ectropion score.
10. Assess local tolerance
11. Record AEs and review diary.
12. Perform a 12-lead ECG.
13. Perform a urine pregnancy test for WOCBP.
14. Collect blood and urine for routine laboratory tests (subject must be fasting at least 8 hours) and coagulation panel.
15. Collect a PK blood sample (all subjects)
16. Collect returned study drug tubes; confirm study drug compliance by weighing returned kits (tubes and boxes, but not leaflets) and reviewing diaries.

10.2.4.7 Follow-up Evaluation – Open-Label Extension (Day 194 or 14 days after End of Open label Treatment/Visit 11)

At 14 days after the last administration of the IP, the following procedures will be performed:

1. Perform a limited physical examination.
2. Record vital signs (blood pressure and pulse).
3. Record any concomitant medications/therapies.
4. Record IGA.
5. Record VIIS.
6. Assess roughness.
7. Record palm/sole assessment.
8. Record palm/sole assessment of fissuring.
9. Record ectropion score.
10. Assess and record AEs occurring since the last evaluation and review diary.
11. Perform a urine pregnancy test for WOCBP.

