10.3.4.1.3 Evaluation of Clinical Laboratory Values

The normal ranges of values for the clinical laboratory assessments in this study will be provided by the responsible laboratory and submitted to Mayne Pharma LLC prior to beginning the study. They will be regarded as the reference ranges on which decisions will be made.

If a laboratory value is out of the reference range, it is not necessarily clinically significant. The investigator must evaluate the out-of-range values and record his or her assessment of the clinical significance in the appropriate eCRF.

All clinical laboratory values that in the investigator's opinion show clinically significant or pathological changes during or after termination of treatment must be reported as AEs and followed, as described in Section 11.2.5.

All measurements described in this section are recognized standard methods.

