10.3.4.2.2 Twelve-lead Electrocardiogram

A standard 12-lead ECG will be performed after the subject has been supine for at least 5 minutes. All ECG recordings will be identified with the subject number, date, and time of the recording. Gel ECG electrodes may be used for ECGs because they are more conductive and cause less trauma on compromised skin. Efficacy assessments should be conducted before ECGs to avoid possible artefact/changes from the ECG.

For subjects in the PK substudy, additional ECGs will be performed postdose during serial blood sampling on Day 1 and Day 30.

If there is a marked prolongation of the QT/QTc interval during treatment, a subject should be discontinued from the IP but remain in the study until full resolution of the event. The DSMB will be informed immediately of such an occurrence.

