11.2. Event Assessment and Follow-up of Adverse Events

The occurrence of an AE or SAE may come to the attention of study personnel during study visits and interviews of a study participant presenting for medical care or upon review by a study monitor.

All reported AEs, including local and systemic AEs not meeting the criteria for SAEs, will be captured on the appropriate eCRF. Information to be collected includes event description, time of onset, clinician's assessment of severity, relationship to study product (assessed only by those with the training and authority to make a diagnosis), and time of resolution/stabilization of the event. All reported AEs occurring while on study must be documented appropriately regardless of relationship. All reported AEs will be followed to adequate resolution.

Any medical condition that is present at the time that the participant is screened will be considered as baseline and not reported as an AE. However, if the study participant's condition deteriorates at any time during the study, it will be recorded as an AE.

Changes in the severity of a reported AE will be documented to allow an assessment of the duration of the event at each level of severity to be performed. AEs characterized as intermittent require documentation of onset and duration of each episode.

Study clinic personnel will record all reportable events with start dates occurring any time after informed consent is obtained until 14 (for nonserious AEs) or 30 days (for SAEs) after the last day of study participation. At each study visit, the investigator will inquire about the occurrence of AE/SAEs since the last visit. Events will be followed for outcome information until resolution or stabilization.

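### Section 11.2.5 ends follow-up of every AE, SAEs included, 14 days after the last dose, while Section 11.2 requires follow-up to resolution or stabilization

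*Protocol*

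**What the plan says.** Two sections of the current text (Amendment 3) govern how long an adverse event is followed.

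- **Section 11.2.5:** "Any AE will be followed (up to a maximum of 14 days after the last dose of IP"). Within that limit, follow-up runs to resolution, stability or another explanation. SAEs are not mentioned separately.
- **Section 11.2:** "All reported AEs will be followed to adequate resolution", and later "Events will be followed for outcome information until resolution or stabilization". Neither sentence has a time limit.

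Section 11.2 also defines which events must be recorded, by start date: from consent "until 14 (for nonserious AEs) or 30 days (for SAEs) after the last day of study participation".

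Other provisions bear on the point:

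- Section 10.2.4.7 (OLE follow-up, Visit 11): "At 14 days after the last administration of the IP, the following procedures will be performed".
- Section 10.2.3: subjects who do not enter the OLE are telephoned "within 14 days after Day 90 to assess any ongoing AEs".
- Section 10.3.4.1.3: clinically significant laboratory changes "must be reported as AEs and followed, as described in Section 11.2.5".
- Section 10.3.4.2.2: on marked QT prolongation, "a subject should be discontinued from the IP but remain in the study until full resolution of the event".

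**The concern.** Both rules govern the same act, following an adverse event to its outcome, and they give different stopping points. A site cannot obey both when an event is unresolved and unstable on day 14 after the last dose. Section 11.2.2.1 describes an SAE as an AE that meets serious criteria, so the limit on any AE covers SAEs.

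The limit runs from the last dose, not the last visit. A subject taken off treatment because of an adverse event therefore starts the 14-day clock on stopping, and this is the subject whose outcome matters most. The cross-reference in Section 10.3.4.1.3 sends clinically significant laboratory changes to the limited rule by name.

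Safety is part of the primary objective (Section 6.1), and Section 11.2.3 asks for a stop date and an outcome for each event. If sites apply different rules, those fields will be incomplete in a way that depends on the site, and some subjects with an unresolved SAE may lose study follow-up.

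**Working it through.** The plan states no figure to reproduce. The check compares the two rules and then places them on one clock.

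**1. Side by side**

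| Event on day 14 after last dose | Section 11.2.5 | Section 11.2 |
|---|---|---|
| Resolved | closed | closed |
| Stable | closed | may be closed |
| Neither resolved nor stable | closed by the limit | follow-up continues |

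The conflict lies in the last row.

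**2. Timeline, in days after the last dose**

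Inputs: limit at day 14 (11.2.5); recording windows of 30 days for SAEs and 14 days for nonserious AEs after the last day of participation (11.2); OLE follow-up visit at day 14 (10.2.4.7).

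*OLE subjects*, taking Visit 11 as the last day of participation (an assumption, since the protocol does not define that day for the individual subject):

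- The SAE window after participation ends at 14 + 30 = day 44 and covers days 15 to 44. All 30 days lie after the limit.
- The nonserious window ends at 14 + 14 = day 28 and covers days 15 to 28. All 14 days lie after the limit.
- With the last dose at about Day 180, the limit falls on Day 194, and recording runs to Day 224 for SAEs and Day 208 for nonserious AEs.

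*Subjects not entering the OLE*, assuming the last dose at about Day 90 and participation ending P days later, with P from 0 to 14:

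- The SAE window ends on day 30 + P, so the part after the limit is 30 + P − 14 days: 16 days for P = 0 and 30 days for P = 14.

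**3. Treatment-emergent events**

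Section 11.1.6 counts events with onset up to 14 days after the last application. An event starting on day k after the last dose (k ≤ 14) can be followed for at most 14 − k days under the limit: 7 days for k = 7 and 0 days for k = 14.

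**4. Does another section lift the limit?**

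- Section 11.2.6.1 asks for follow-up SAE information to be sent on, but sets no duration for obtaining it.
- Section 11.2.6.2 removes the time limit on reporting suspected serious ADRs. It concerns reporting, and only those events.
- Section 11.3.2 follows pregnancies to delivery or termination, which is a special case.
- Section 10.3.4.2.2 covers marked QT prolongation only, and its rule itself conflicts with the limit.

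None of these lifts the limit for SAEs in general.

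**The case against.** The strongest case is that the practical conflict is narrow.

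- **The 14- and 30-day windows concern when an event starts.** They are not follow-up rules and do not themselves contradict Section 11.2.5. For an event that starts after day 14, the sentence in Section 11.2 on following events is a workable instruction. This is right as far as it goes: the contradiction is about follow-up duration. The windows show only that the limit can expire before a recordable SAE begins.
- **The end of participation is inferred.** Equating Visit 11 with the last day of participation is an assumption. It affects the day ranges but not the conflict.
- **There is a second definition of treatment-emergent.** Section 13.1.6.2 runs the window to the follow-up or early termination visit, whichever comes first, so for early terminators it can close before day 14. The arithmetic in step 3 therefore holds under Section 11.1.6 and not in every case.
- **A specific rule normally overrides a general one.** On that reading the QT provision prevails and protects the subject. That is plausible, but the protocol does not say so, and it does not help other SAEs.
- **There are safeguards.** Serious events can be updated on follow-up forms, open events can be coded as ongoing or not recovered (Sections 11.2.3 and 11.2.2.4), and the events expected are mainly application site reactions (Section 11.3.1). These soften the consequence but leave the limit in place.

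The direct conflict between Sections 11.2 and 11.2.5 for events still unresolved and unstable on day 14 survives all of these points.

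**Conclusion.** The concern holds. Section 11.2.5 limits follow-up of every AE, SAEs included, to 14 days after the last dose. Section 11.2 twice requires follow-up with no time limit, and no precedence is stated.

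The events directly affected are those neither resolved nor stable on day 14. Under the assumptions above, SAEs starting on about days 15 to 44 after the last dose in the OLE must also be recorded but have no required follow-up under Section 11.2.5. Outside the OLE, 16 to 30 of the 30 days of the SAE window lie beyond the limit. The protocol gives no basis for estimating how many events this will involve.

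The effect is on the completeness of outcome and duration data and on the care of subjects with unresolved events. The efficacy analysis, the sample size and the incidence of treatment-emergent events are unaffected. The wording should be corrected, but the matter does not threaten the trial's main conclusions.

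**What to change.** Delete the parenthesis with the 14-day maximum from Section 11.2.5, so that it agrees with Section 11.2 and all events are followed to resolution or stabilization. If the sponsor wants a limit for nonserious AEs, it should be stated identically in both sections, with SAEs expressly excluded. Setting that limit no earlier than the end of the recording window (about day 28 after the last dose in the OLE) would be tidy, but it is a preference and not needed to remove the contradiction.

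The change is one sentence and asks for no follow-up beyond what Section 11.2 already requires. Sites that have been working to the 14-day limit would have more to do. Under Sections 14.8 and 16.3 it needs a formal amendment with IRB/IEC approval, so it is best included with the next planned amendment.
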